### 5.4 Statistical Analysis

#### 5.4.1 Sample Size and Justification

This is a retrospective cohort study; sample size is not based on a pre-specified effect size. All eligible patients with breast PT from the eight centers between January 1, 2001, and December 31, 2023, will be included. Based on each center’s historical annual

caseload and pathology database searches, approximately **3,500 patients** are expected (benign:borderline:malignant  $\approx$  7:2:1).

This sample size is the largest multicenter real-world study in the PT field to date. According to the EPV (events per variable) rule, with local recurrence as the primary endpoint (estimated overall recurrence rate  $\sim$ 11%, yielding  $\sim$ 380 events), the sample size supports multivariable analysis of 30–40 independent variables, fully meeting the requirements for prognostic factor screening.

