#### **2.2.4 Prognostic Factors**

Domestic and international studies consistently agree that WHO histological grade (benign, borderline, malignant) is the most important prognostic factor. Higher grade is associated with greater risks of recurrence and metastasis. In addition, margin status, stromal overgrowth, tumor size, and patient age have also been identified as key factors affecting local recurrence [18-20]. Sun Yat-sen Memorial Hospital, Sun Yat-sen University, previously developed and validated a nomogram based on clinical and pathological factors from 334 PT cases using Cox regression to assist in evaluating PT prognosis, with external validation [21]. Benign PT does not significantly affect overall survival, so survival-related prognostic models mainly focus on borderline and malignant PT [9,22].

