##### **3.1.3 Exploratory Objectives**

(1) Analyze recurrence event patterns: To analyze the time distribution of recurrences, number of recurrences, and probability of pathological grade progression after recurrence, providing clinical insights into tumor progression mechanisms.

(2) Identify independent prognostic factors: To screen independent risk factors for local recurrence, distant metastasis, and survival using multivariable regression methods, and to compare differences in prognostic factors across pathological grades, providing evidence for personalized follow-up and treatment decisions.

(3) Lay the foundation for prospective studies: The database generated from this study will provide hypotheses and a theoretical framework for future prospective, interventional clinical research.

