## **5. Study Design**

### **5.1 Overall Design**

[figure not shown]
This is a multicenter, retrospective cohort study. Data will be collected from patients who underwent breast surgery at the Departments of Breast Surgery of the following eight participating centers between January 1, 2001, and December 31, 2023:

- Sun Yat-sen Memorial Hospital, Sun Yat-sen University
- The First People's Hospital of Foshan
- Sun Yat-sen University Cancer Center
- Peking University Shenzhen Hospital
- Foshan Women and Children's Hospital
- The First Affiliated Hospital of Guangzhou Medical University
- Zhongshan People's Hospital
- Shanwei People's Hospital

The expected sample size is approximately 3,500 patients. Using real-world data over nearly 20 years, the study will systematically describe the clinicopathological characteristics, treatment patterns, and long-term prognosis of breast PT in China, and identify independent risk factors through descriptive analysis, propensity score methods, competing risk models, and sensitivity analyses.

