### **(4) Statistical adjustments**

- Multivariable model variable selection: backward stepwise regression (based on AIC) or LASSO penalized regression (when many variables).
- Proportional hazards assumption: tested using Schoenfeld residuals. If violated, stratified Cox, time-dependent covariates, or accelerated failure time models will be used.
- Multiple comparisons: For three primary endpoints (LR, DM, OS), each will be analyzed separately without multiple correction. For multiple exposure comparisons within the same endpoint, Bonferroni correction will be applied.

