### **(5) Bias control (as described in 5.3) – PSM, IPTW, E-value.**

### **(6) Stratified, subgroup, and sensitivity analyses**

- **Stratified analysis:** All primary analyses will be stratified by pathological grade (benign/borderline/malignant) to compare prognostic factors across grades.
- **Pre-specified subgroups:** Age (<35 vs. ≥35 years), tumor size (<5 cm vs. ≥5 cm), surgical procedure (segmental resection vs. minimally invasive rotary

excision, wide local excision vs. total mastectomy). Forest plots will display subgroup HRs with interaction P-values.

- **Sensitivity analyses:**
  - Complete case analysis vs. multiple imputation.
  - Varying PSM parameters (1:1 vs. 1:2 matching, caliper 0.1 vs. 0.2).
  - Separate analysis of recurrence definitions (ipsilateral chest wall/axilla only) to exclude misclassification.
  - Excluding patients with follow-up <6 months.
  - For OS, competing risk analysis with death from PT vs. other causes.

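### The events-per-variable justification for 30–40 variables covers pooled local recurrence only; it fails for local recurrence within each grade and for distant metastasis in malignant tumours, and is not shown for pooled metastasis or survival

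*Combined protocol and SAP*

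**What the plan says.** Section 5.4.1 sets no effect size. It takes every eligible patient, expects about 3,500 with a grade mix of "benign:borderline:malignant $\approx$ 7:2:1", and applies an EPV rule to LR: "estimated overall recurrence rate $\sim$ 11%, yielding $\sim$ 380 events". It concludes that "the sample size supports multivariable analysis of 30–40 independent variables, fully meeting the requirements for prognostic factor screening". No EPV threshold is stated, and no event count is given for DM, for OS or for any single grade.

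The planned modelling is wider than that basis:

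- Section 3.1.3 (2) sets out to "screen independent risk factors for local recurrence, distant metastasis, and survival using multivariable regression methods", and to compare the factors between grades.
- Section 5.4.2 (2) places Cox regression under the primary endpoints for LR, DM and OS alike.
- Section 5.4.2 (3) brings the secondary-endpoint variables into Cox or logistic models as covariates.
- Section 5.4.2 (4) selects variables by backward AIC, or by LASSO if there are many. It does not say how many is many.
- Section 5.4.2 (6) states: "All primary analyses will be stratified by pathological grade (benign/borderline/malignant) to compare prognostic factors across grades".

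**The concern.** The number of parameters a Cox model can carry depends on the events in that model, not on the patients in the database. The calculation is made once, for the endpoint and population with the best-documented event count, and its conclusion is then worded as if it covered all the prognostic screening. Splitting by grade divides the 380 events three ways, and the malignant group, where the outcome matters most clinically, is the smallest.

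If variables are selected separately in each grade on too few events, the models will be overfitted and the selected sets unstable. A factor retained in one grade and dropped in another would then be read as a difference between grades, although no test of difference has been made. That comparison is the stated purpose of the stratified analysis.

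**Working it through.** **Inputs.** Cohort of 3,500 and mix of 7:2:1 (section 5.4.1), so 2,450 benign, 700 borderline and 350 malignant. Recurrence rates of 7.1%, 16.7% and 25.1% (section 2.2.2). DM in malignant tumours of 6.5% to 62.5%, the highest of the grades (section 2.1). Formulas: events = patients × rate; maximum parameters = events / EPV, rounded down.

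**1. The plan's own figure.** 3,500 × 0.11 = 385. From the grade rates: 2,450 × 0.071 + 700 × 0.167 + 350 × 0.251 = 173.95 + 116.9 + 87.85 = 378.7, or 10.8%. Both agree with about 380. Then 380/30 = 12.7 and 380/40 = 9.5, so the implied EPV is about 10, and 380/10 = 38 parameters. The pooled LR statement reproduces.

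**2. LR within grade.**

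| Grade | LR events | Parameters at EPV 10 | EPV with 30 to 40 variables |
|---|---|---|---|
| Benign | 174 | 17 | 5.8 to 4.3 |
| Borderline | 117 | 11 | 3.9 to 2.9 |
| Malignant | 88 | 8 | 2.9 to 2.2 |

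No grade reaches 30.

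**3. The covariates the plan lists.** Section 3.2.2 names 15 variables. Grade drops out within a stratum, leaving 14, and section 3.2.3 adds history of other malignancy, making 15. Tumour location has three levels (one extra parameter) and the four named procedures need three parameters (two extra). With imaging findings counted as only one, the total is 15 + 1 + 2 = 18. EPV for LR is then 174/18 = 9.7 in benign, 117/18 = 6.5 in borderline and 88/18 = 4.9 in malignant tumours.

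**4. DM in malignant tumours.** 350 × 0.065 = 22.75 and 350 × 0.625 = 218.75, so 23–219 events and 2–21 parameters. Thirty parameters would need 300/350 = 85.7% of these patients to metastasise, above the top of the cited range.

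**5. Pooled DM.** Thirty parameters need 300 events: 300/3,500 = 8.6%. If malignant DM is 6.5% and no grade exceeds it, the ceiling is 3,500 × 0.065 = 227.5, about 228 events or 22 parameters. If malignant DM is 62.5%, the other 3,150 patients must supply 300 − 218.75 = 81.25 events, a rate of 2.6%. The documents give no rate for them.

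**6. Pooled OS.** The documents give no death rate. Purely as assumptions: 2% deaths gives 70 events (7 parameters), 5% gives 175 (17), 8.6% gives 301 (30) and 10% gives 350 (35).

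**The case against.** The best defence is that section 5.4.1 names LR as its basis, that its arithmetic is right, and that nothing in the plan commits 30–40 variables to a DM, OS or single-grade model. All of that is true. The fault is therefore not a miscalculation; it lies in the general conclusion and in the missing counts. Nor does it depend on 30–40 variables being entered, since the roughly 18 parameters in the plan's own list already exceed capacity clearly in borderline and malignant tumours, and marginally in benign.

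Other replies have partial force:

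- LASSO is allowed, and shrinkage does address overfitting. But backward AIC is offered as an alternative, and no rule says which applies.
- Stratified could mean separate baseline hazards in one Cox model. That alone would not compare factors between grades, which is the stated aim and requires separate fits or interactions.
- The threshold is not stated. At EPV 5, benign LR would support 34 parameters (borderline 23, malignant 17). That is not the threshold the plan's figures imply, and two of the three grades would still fall short of 30.
- Factor screening is an exploratory objective, and the sample size does not rest on this sentence. However, section 5.4.2 (2) also puts the multivariable models under the primary endpoints.

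A reader might infer that the claim fails for pooled OS, because section 2.2.4 says "Benign PT does not significantly affect overall survival" and section 2.1 calls death a rare event. The documents do not support that inference. OS counts deaths from any cause in patients operated on from 2001 to 2023, and no death rate is given.

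**Conclusion.** The point holds in a limited form. The 30–40 statement is supported for pooled LR. It does not hold for LR in any grade (17, 11 and 8 parameters) or for DM in malignant tumours (2–21). For pooled DM and pooled OS it is not shown. Failure for pooled DM looks likely on the cited figures but is not excluded; for pooled OS the documents do not allow a judgement either way.

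This rests on the plan's expected mix and cited rates applying to this cohort, on crude proportions standing in for events observed during follow-up, and on an EPV of about 10, which the figures imply.

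Two further inferences would go too far. The documents do not require benign tumours to be left out of the DM and OS models; that would change the target population and is a design choice. Nor is the tendency of stepwise AIC to keep chance predictors evidence that this sample is too small, since the expected number kept by chance depends on the number of candidates rather than on the events.

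The descriptive rates, Kaplan-Meier curves and cumulative incidence estimates are unaffected.

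**What to change.** Before database lock, revise sections 5.4.1 and 5.4.2 as follows.

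1. Limit the 30–40 statement to pooled LR and state the EPV threshold. Add a table of expected events and maximum candidate parameters by endpoint and grade. At EPV 10, LR reads 38 pooled and 17, 11 and 8 by grade. Malignant DM reads 2–21, which must not be used as the cap for a model that also includes other grades. Set the DM and OS caps from the observed event counts before any modelling.
2. Compare prognostic factors between grades by grade-by-factor interaction tests in the pooled LR model, for a short pre-specified list, instead of separate stepwise selection in each grade. Keep the total within the cap. The 18 parameters above plus 2 for grade make 20, leaving 38 − 20 = 18. A one-parameter factor uses two interaction terms, so at most nine such factors fit. Interactions for every covariate would not: 20 + 2 × 18 = 56.
3. Where the candidate list exceeds the cap (borderline and malignant LR, and DM or OS as the counts dictate), use a short pre-specified model or a penalised one, not backward AIC.

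This changes text only and needs no new data. The stated capacity becomes less favourable, and the smaller models may consider fewer candidate variables.

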#### **5.4.2 Statistical Analysis Plan**

Statistical analyses will be performed using R version 4.2.0 or higher (key packages: tidyverse, survival, rms, tableone, MatchIt, mice, tidycmprsk, mstate, etc.). The significance level  $\alpha = 0.05$  (two-sided), and 95% confidence intervals will be reported.

##### **(1) Descriptive analysis**

- **Demographic and clinicopathological characteristics:** Continuous variables will first be tested for normality (Shapiro-Wilk test). Normally distributed variables will be presented as mean  $\pm$  SD, with group comparisons using t-test or ANOVA; non-normally distributed variables as median (IQR), with group comparisons using Mann-Whitney U or Kruskal-Wallis test. Categorical variables as frequency (%), with group comparisons using Pearson  $\chi^2$  test or Fisher's exact test (when expected frequency  $<5$ ).
- **Treatment patterns:** Distributions and temporal trends (e.g., by 5-year intervals) of surgical procedures, margin status, lymph node surgery, and adjuvant radiotherapy/chemotherapy will be described, stratified by pathological grade and time period.
- **Outcome events:** Local recurrence rate, distant metastasis rate, and tumor-specific mortality rate will be calculated for the overall cohort and by pathological grade. Time to recurrence, number of recurrences, and proportion/probability of grade progression after recurrence will be described.

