## 2. Background

### 2.1 Overview of Breast Phyllodes Tumor

Phyllodes tumor (PT) of the breast is a rare fibroepithelial neoplasm composed of both stromal and epithelial components, accounting for less than 1% of all breast tumors [1]. Clinically, it typically presents as a rapidly growing, painless mass. According to the World Health Organization (WHO), PT is classified into three grades based on histological features: benign, borderline, and malignant, with reported recurrence rates of 7.1%, 16.7%, and 25.1%, respectively [2]. The median/mean age at diagnosis ranges from 36.4 to 55 years, and the mean tumor size ranges from 3.7 to 11.3 cm. Malignant PT has the highest rate of distant metastasis, ranging from 6.5% to 62.5%, primarily via hematogenous spread, with the lungs and bones being the most common sites [3].

Because PT is rare, large-scale studies on its etiology, diagnosis, treatment, and prognosis are very limited. PT can grow very rapidly; delayed diagnosis and treatment may allow the tumor to become so large that surgery is no longer an option. Current imaging modalities (ultrasound, mammography, MRI) have limited ability to differentiate PT from other breast lesions and to accurately predict histological grade. Moreover, due to the often large tumor size and significant intratumoral heterogeneity, small needle biopsy samples may not fully represent the entire lesion, so accurate histological grading still relies on complete pathological evaluation of the excised tumor. PT is not sensitive to radiotherapy or chemotherapy; the mainstay of treatment is complete surgical excision [4]. The efficacy of adjuvant therapies such as targeted therapy and immunotherapy in PT requires further investigation. Although histological grade can, to some extent, predict patient outcomes, some benign PT may recur repeatedly or even undergo malignant transformation, whereas some malignant PT may remain stable for long periods. The current grading system does not fully explain individual differences in prognosis.

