##### **3.1.2 Secondary Objectives**

(1) Describe distribution characteristics: To determine the proportion of benign, borderline, and malignant PT in the Chinese population, as well as the distribution patterns of demographic and clinical features.

(2) Evaluate current treatment patterns: To depict the landscape and temporal trends of surgical procedures, margin status, lymph node surgery, and adjuvant radiotherapy/chemotherapy for PT in China over the past two decades.

(3) Quantify prognostic outcomes: To calculate local recurrence rates, distant metastasis rates, and tumor-specific mortality rates for the overall cohort and by histological grade, and to describe the patterns of PT outcomes.

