5.2 Study Flow Diagram

### 5.3 Methods to Reduce Bias

(1) **Standardized data collection** – All data extractors at participating centers will receive uniform training. Standardized Case Report Forms (CRFs) will clearly define each variable (e.g., “positive margin” defined as tumor cells present at the margin on pathology; “local recurrence” requires pathological confirmation) to reduce measurement and information bias.

(2) **Double independent extraction of key variables** – For primary outcome variables (recurrence, metastasis, death) and key exposure variables (pathological grade, surgical procedure, margin status), two researchers will independently extract data and cross-validate. Discrepancies will be adjudicated by a third senior researcher.

(3) **Clear inclusion/exclusion criteria** – Strict definitions will avoid selection bias. All eligible consecutive cases will be enrolled; no sampling based on outcome or exposure.

(4) **Handling of missing data** – Cases with >20% missing key variables will be excluded. For variables with  $\leq 20\%$  missingness, multiple imputation ( $m=5$ ) will be used. Results from complete case analysis and imputed analysis will be compared to assess missingness bias.

(5) **Confounding control** – Multivariable regression models will adjust for known prognostic factors (age, tumor size, pathological grade, margin status, etc.). For non-randomized treatment comparisons (e.g., different surgical procedures), propensity score matching (PSM, caliper =  $0.2 \times \text{SD of PS}$ ) or inverse probability of treatment weighting (IPTW) will be used to balance covariates. E-values will be calculated to evaluate the strength of unmeasured confounding.

(6) **Control of multicenter heterogeneity** – Center effects will be adjusted using Cox shared frailty models or generalized estimating equations (GEE) with center as a random effect.

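### Treatment trends for 2001–2023 are described by grade and period pooled over eight centres, with no centre adjustment tied to them, so a change in centre mix can read as a change in practice

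*Combined protocol and SAP*

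**What the plan says.** Section 3.1.2, secondary objective (2), is worded as a trend: "To depict the landscape and temporal trends of surgical procedures, margin status, lymph node surgery, and adjuvant radiotherapy/chemotherapy for PT in China". The cohort covers surgery at eight centres "between January 1, 2001, and December 31, 2023" (section 5.1).

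The analysis that serves this objective is the treatment-patterns item of section 5.4.2 (1). It offers 5-year intervals as an example of the time axis and says that procedures, margin status, "lymph node surgery, and adjuvant radiotherapy/chemotherapy will be described, stratified by pathological grade and time period". It names no centre stratum, no model with calendar year and no trend test.

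Two other places bear on it:

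- Section 5.4.2 (3) sends treatment characteristics to the between-group comparisons of 5.4.2 (1). For categorical variables these are Pearson chi-square or Fisher's exact test. The regressions added in (3) use the treatment variables as covariates for the primary outcomes, not as outcomes of calendar time.
- Section 5.3 (6) states: "Center effects will be adjusted using Cox shared frailty models or generalized estimating equations (GEE"), with centre as a random effect. It does not say which analyses this covers.

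**The concern.** A proportion pooled over centres is a weighted average of the centres' own proportions, weighted by each centre's share of the patients in that period. It moves when practice moves, and also when the shares move. The planned tables cannot separate the two.

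A shift in shares is plausible here. The eight centres are of different kinds: a cancer centre, a women and children's hospital, and general hospitals. Section 4.1 requires reasonably complete records and follow-up data, and section 4.2 excludes patients lost to follow-up or with missing critical data. If older records survive better at some centres than at others, the early periods will over-represent those centres. Growth in caseload at some centres would have a similar effect.

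At stake is the reading of objective (2). A fall in mastectomy or a rise in adjuvant treatment could be reported as a change in national practice when only the contributors changed. This applies to pure description as much as to testing. The analyses of local recurrence, distant metastasis and overall survival are not affected.

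**Working it through.** **The plan's own figures.** Section 5.4.1 states that "approximately 3,500 patients are expected", with grades in the ratio 7:2:1 and about 380 local recurrences at about 11%. These reproduce: 3,500 × 0.11 = 385. From the grade-specific rates in section 2.1, 0.7 × 7.1% + 0.2 × 16.7% + 0.1 × 25.1% = 10.82%, or 379 events. They concern recurrence, and the plan gives no rate, effect size or power for treatment trends. What carries over is the size of the grade strata: 2,450 benign, 700 borderline and 350 malignant.

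**Drift from centre mix.** Treatment rates and centre shares are not in the documents, so all values here are assumptions. Take two groups of centres with constant rates a and b, the first contributing share s. The pooled rate is s·a + (1 − s)·b. With a = 40% and b = 15%:

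| Share of first group | Early pooled rate | Late pooled rate |
|---|---|---|
| 80% to 40% | 0.8 × 0.40 + 0.2 × 0.15 = 35% | 0.4 × 0.40 + 0.6 × 0.15 = 25% |
| 50% to 40% | 0.5 × 0.40 + 0.5 × 0.15 = 27.5% | 25% |

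With an assumed 300 early and 900 late patients, the first row gives a Pearson chi-square of 0.10² / [0.275 × 0.725 × (1/300 + 1/900)] = 11.3, p = 0.0008. The second gives 0.025² / [0.25625 × 0.74375 × (1/300 + 1/900)] = 0.74, p = 0.39. Practice is constant in both.

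A second example uses rates of 30% and 10%, equal yearly caseload, a share that changes linearly over 23 years, and five bins (the last of three years). The table gives the probability of a significant result at two-sided 0.05 with no change in any centre.

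| Share of first group | Crude rate, first to last bin | Stratum | Pearson, 4 df | Crude 1-df trend test |
|---|---|---|---|---|
| 70% to 40% | 23.5% to 18.3% | All 3,500 | 51% | 73% |
| 70% to 40% | same | Benign | 37% | 58% |
| 70% to 40% | same | Borderline | 13% | 21% |
| 70% to 40% | same | Malignant | 8.5% | 13% |
| 50% to 40% | 19.8% to 18.1% | All 3,500 | 9% | 14% |

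The false signal thus runs from near nominal to more likely than not, depending on how far the shares move. An ordered test without centre makes it worse, because it is more sensitive to the spurious drift.

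**Secondary point: order of the periods.** Pearson and Fisher tests ignore order. For a linear trend that a 1-df test detects with 80% power at two-sided 0.05, the noncentrality is 7.85. At that noncentrality the omnibus test has 59.5% power on 4 df (five bins) and 64.5% on 3 df (four bins), a loss of 20.5 or 15.5 points. With assumed changes, equal yearly caseload and five bins:

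| Stratum | Change | Pearson, 4 df | 1-df trend |
|---|---|---|---|
| All 3,500 | 10% to 20% | 98.6% | 99.8% |
| All 3,500 | 20% to 30% | 91.7% | 98.1% |
| All 3,500 | 10% to 15% | 53.8% | 75.1% |
| Borderline | 10% to 20% | 38.0% | 58.9% |
| Malignant | 30% to 50% | 40.2% | 61.5% |

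The loss is about 1 to 6 points for a 10-point change in the whole cohort, and about 20 points where power is middling, mainly in the two smaller strata or for small changes.

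**The case against.** Four arguments can be made for the plan.

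1. *The objective is descriptive.* The treatment-patterns item says trends will be described and names no test. A reader might infer from section 5.4.2 (3) that periods will be compared by chi-square, but that section does not say that the groups are calendar periods. This stands: one can say only that the tests named for these variables ignore order, not that they will be used on the periods. It does not answer the centre-mix problem, which affects a described proportion just as much.
2. *Centre is already handled.* Section 5.3 (6) is unrestricted, and GEE suits binary variables such as treatment use. This stands in part: the scope is unspecified rather than excluded. But a Cox frailty model cannot be applied to treatment proportions, no GEE of treatment on calendar year is specified, and a GEE that only clusters on centre would not by itself take a shift in centre shares out of the year effect.
3. *The size is assumed.* This stands. A share falling from 50% to 40% does little harm.
4. *The power loss is conditional.* This stands. A reader might infer that the study as a whole loses 20 points of power for trends. The documents do not support that: the bins are only an example, no power is claimed for these analyses, and the loss nearly vanishes for a 10-point change in the full cohort.

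A full set of centre-adjusted models within grade would also meet sparse cells, above all among about 350 malignant cases. The fix must allow for this.

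**Conclusion.** The concern holds as a gap in the plan for one secondary objective. Trends are to be described by grade and period, pooled over eight unlike centres, and no centre adjustment is tied to them. A changing centre mix could therefore be reported as a change in practice. The drift depends on two things the documents do not give: how much treatment rates differ between centres and how far their shares move. In the assumed examples with rates of 40% and 15%, it runs from 2.5 to 10 percentage points. The documents do not show that shares did change, so the claim is that the planned analysis cannot rule this out, not that the trends will be wrong.

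The order-blind tests are a lesser matter, relevant only if periods are tested. The change is worth making because it is cheap and uses data already being collected.

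**What to change.** In section 5.4.2 (1), under treatment patterns:

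1. Report patient counts by centre and period, so that the reader can see whether the mix changes.
2. Give centre-standardised proportions beside the crude ones, with fixed weights over the centres that contribute in all the periods compared.
3. Base any statement about a change in practice on the calendar-year effect from a logistic model (multinomial for procedure) that includes centre. Fit it overall with grade as a covariate, and within grade where numbers allow. In the malignant stratum, collapse sparse categories or use penalised or random centre effects.
4. If periods are tested, use the 1-df year effect from that model rather than a Pearson or Fisher test across bins. A trend test without centre is not a substitute.
5. State in section 5.3 (6) whether its centre adjustment extends to the treatment trends.

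The cost is some wording and a few more models, with no new data. The downside is less precise estimates in small strata. Centres that do not contribute in every compared period also drop out of the standardised figures, which should be said beside the table.

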### **2.2.2 Epidemiology**

PT accounts for less than 1% of all breast tumors, and its epidemiological characteristics show distinct racial, regional, and age differences. As early as 1987, Chua et al. noted that PT incidence is higher in non-white populations, particularly in Asian women [13]. Asian PT patients are often younger (peak age 25-30 years), while Western patients are typically in their 40s. In 1993, Bernstein et al. reported that Latinas have a higher risk of PT compared to other racial groups. Age distribution varies by race, with Asian and Latina patients being significantly younger on average than non-Latina white patients [14]. Moten and Goldberg, in a large analysis of 1,202 patients with malignant PT from the SEER database, found that minority groups (Black, Hispanic, Asian) were diagnosed at significantly younger ages and had a higher risk of large tumors (>5 cm) and tumor extension beyond breast tissue [15].

Multiple studies show that the incidence of PT is approximately 2.1 per million women, accounting for 0.3%-1.0% of all breast tumors, with age at diagnosis concentrated between 35 and 55 years (median 45 years). Histologically, about 60%-75% of PT are benign, but both benign and malignant PT have the potential for local recurrence [3,5,6]. A systematic review and meta-analysis by Yu et al. of 52 real-world studies found an overall recurrence rate of approximately 12.6%, with risk increasing significantly with higher pathological grade: recurrence rates for benign, borderline, and malignant PT were approximately 7.1%, 16.7%, and 25.1%, respectively [10].

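### A one-way summary of grade progression after recurrence cannot separate tumour progression from grading disagreement; report the full initial-by-recurrent grade table

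*Combined protocol and SAP*

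**What the plan says.** Section 5.4.2(1), under outcome events, gives the whole analysis in one line: "Time to recurrence, number of recurrences, and proportion/probability of grade progression after recurrence will be described". The matching objective, section 3.1.3(1), is to analyse the "probability of pathological grade progression after recurrence, providing clinical insights into tumor progression mechanisms". Section 2.2.5 lists the same item among the gaps in current research.

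None of these places mentions downgrades, unchanged grades or a cross-table. Progression has no stated denominator, and the plan does not say whether the first or any recurrence counts.

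Both grades are taken from existing records. Section 6.1.2 draws all data from hospital information systems, including the pathology system, and section 3.2.1(1) relies on pathology reports to confirm recurrence. Surgery dates run from 2001 to 2023 at eight centres (section 5.1). Grade follows WHO criteria, with no edition fixed (sections 3.2.2(10) and 4.1(1)).

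The safeguards on grade are extractor training and double extraction (section 5.3(1) and (2)) and 10% source data verification (section 6.2.3). They control how a reported grade is transcribed. None addresses whether two pathologists, or one pathologist at two times, would grade the same tissue alike.

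**The concern.** A grade change between two reports can mean that the tumour changed or that the readings disagreed. A count of upgrades alone adds the two together. The problem is sharpest for benign tumours: nothing lies below benign, so every disagreement that follows a benign first label is counted as progression. The disagreements that run the other way, such as a borderline first label followed by a benign one, fall outside the summary.

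At stake is how an exploratory result is read. Section 5.4.1 describes this as the largest multicentre real-world study in the field, so a progression probability from it is likely to be quoted, and section 3.1.3(1) already attaches a mechanistic reading to it.

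**Working it through.** **Inputs from the documents**
- Cohort: about 3,500 (section 5.1), with benign, borderline and malignant in the ratio 7:2:1 (section 5.4.1), so 2,450, 700 and 350 patients.
- Recurrence by grade, section 2.2.2: "recurrence rates for benign, borderline, and malignant PT were approximately 7.1%, 16.7%, and 25.1%, respectively".
- The plan's own event count, section 5.4.1: "estimated overall recurrence rate $\sim$ 11%, yielding $\sim$ 380 events".

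**The plan's event count reproduces**
- 3,500 x 0.11 = 385.
- Weighted by grade: 2,450 x 0.071 = 174.0; 700 x 0.167 = 116.9; 350 x 0.251 = 87.9. The total is 378.7.
- Both agree with about 380.

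**Illustration with no true grade change**

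Assumptions, none of them in the documents:
- The three counts above are the true grades of the recurrences.
- Each reading is wrong by one grade with probability e.
- A misread borderline tumour goes up or down equally often (e/2 each).
- The two readings err independently and with the same error rates.

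The expected count with first label i and second label j is the sum over true grades t of n(t) x p(i given t) x p(j given t).

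Worked at e = 10%:
- First label benign: 173.95 x 0.90 + 116.9 x 0.05 = 162.4.
- Benign at both readings: 173.95 x 0.90² + 116.9 x 0.05² = 141.2.
- Apparent upgrades: 162.4 - 141.2 = 21.2, and 21.2 / 162.4 = 13.1%.

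| Error per reading (assumed) | Benign-labelled recurrences that appear to progress | Upgrades / downgrades, all grades |
|---|---|---|
| 2% | 2.7% (5 of 172) | 7 / 7 |
| 5% | 6.6% (11 of 168) | 18 / 18 |
| 10% | 13.1% (21 of 162) | 34 / 34 |
| 15% | 19.3% (30 of 157) | 49 / 49 |
| 20% | 25.4% (38 of 151) | 62 / 62 |

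**Sensitivity of the illustration**
- If a borderline tumour can be misread with probability e in each direction, the figures at 2%, 5%, 10% and 20% are 3.3%, 8.1%, 15.6% and 28.6%.
- If in half of the recurrences both readings carry the same label, right or wrong, every figure halves: 3.3%, 6.5% and 12.7% at 5%, 10% and 20%. Upgrades still equal downgrades.

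**What the full table can and cannot show**

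Upgrades equal downgrades only when the error rates are the same at both readings. Take again no true change, but let the first reading be one grade too low with probability 10% and too high with 5%, and the second reading the reverse. The expected cells are then:
- benign to borderline 26.5, against 12.8 the other way;
- benign to malignant 1.2, against 0.3;
- borderline to malignant 18.3, against 8.9.

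That is about 46 upgrades against 22 downgrades, an excess of about 24. Bowker's statistic at these expected counts is 4.75 + 0.53 + 3.22 = 8.50 on 3 degrees of freedom, p about 0.04.

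The difference can also understate real change. Suppose 15% of benign and borderline recurrences truly move up one grade: 0.15 x (173.95 + 116.9) = 44 patients. With e = 20% at both readings, the expected difference is only about 31.

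**The case against.** The strongest reply is that the documents contain no evidence on how often excision grades disagree. The sentence in section 2.1 that mentions heterogeneity, "due to the often large tumor size and significant intratumoral heterogeneity", is about needle biopsy. It goes on to treat the excised tumour as the basis for accurate grading, and that is the specimen this study uses for the initial grade (section 4.1(1)). Section 4.2(1) also removes uncertain and unclassified grades. This stands: the sentence is not evidence that excision grades are unreliable, and a reader should not infer from it that 7% to 25% is an expected result.

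A reader might also infer that the plan restricts the output to upgrades. It does not. It names progression and is silent on the rest; no table layouts are given for any descriptive output, and section 5.4.2 lists a multi-state package (mstate). Listing a package is not a planned transition analysis, however, so the plan as written commits only to the one-way figure.

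A third tempting inference is that follow-up advice for benign tumours would rest on an artefact. The wording on personalised follow-up belongs to section 3.1.3(2), on prognostic factors, and not to the grade-progression objective.

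Finally, it may be said that an exploratory, descriptive item needs no such care. That limits the weight of the point but does not remove it, because section 3.1.3(1) gives the number an interpretation that it cannot carry.

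**Conclusion.** The point holds as a cheap improvement to an exploratory summary. As written, the plan yields a one-way figure from two routine gradings, with no safeguard against grading variation, and that figure cannot distinguish progression from disagreement. This follows from the structure of the summary and needs no assumed error rate beyond its not being zero.

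The size does rest on assumption. The range of 7% to 25% applies only if each reading is independently wrong by one grade 5% to 20% of the time. A lower error rate or shared errors bring it down, as the sensitivity figures show.

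A reader might go further and take the excess of upgrades over downgrades as the true progression. The documents do not support that: with no WHO edition fixed for surgery over 23 calendar years (2001 to 2023), equal error at both readings cannot be taken for granted. The unequal-error example shows that an excess can arise with no biological change, and the last example shows that it can also understate real change.

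**What to change.** In sections 5.4.2(1) and 3.1.3(1), replace the one-way summary with the following.
- The full 3x3 table of initial grade against grade at first recurrence. The denominator is patients with a first local recurrence and a grade at both times; state how many lack a grade at recurrence.
- Upgrades, unchanged grades and downgrades, overall and by initial grade, with 95% CIs.
- The upgrade-minus-downgrade difference with its 95% CI and a symmetry test (Bowker, or McNemar for each adjacent pair), labelled as descriptive.
- A sentence stating that an excess of upgrades supports progression but neither proves nor quantifies it, because grading criteria or practice may have differed between the two readings.

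Do not adopt a rule that equates the excess with progression.

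The cost is one extra table and one test, provided the grade at recurrence is captured, which the existing objective already requires. The change should be written in before the database lock described in section 6.2.4. The downside is a more cautious statement about progression. The table makes disagreement visible but does not correct for it.
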